2.2 Control Device: Standard of Care (SOC) Long-Term Oxygen Therapy

Long-term oxygen therapy (LTOT) is prescribed for patients whose COPD is considered to be severe. Oxygen is provided continuously to the patient in either a continuous-flow or pulsed delivery pattern.

Long-term oxygen therapy can be provided to patients through stationary LTOT systems including large gas cylinders, large liquid oxygen cylinders, and large oxygen concentrator systems. Some stationary oxygen systems also offer an ambulatory component; an example of this is a small liquid oxygen device which can be trans-filled from the larger container.

For the purposes of this study, patients who are randomized to the control arm may not use a POC device as an ambulatory oxygen option.

3 Study Design

This is a post-approval, randomized, unblinded, multicenter, parallel group design study with patients randomized to either control (SOC long-term oxygen therapy alone [SOC arm]) or active treatment (SOC long -term oxygen therapy plus a POC [POC arm]) in a 1:1 ratio. All patients will be provided with an activity monitor to wear continuously to monitor physical activity, and an oxygen use diary to collect oxygen usage data. Eligible patients have COPD and are prescribed to receive long-term oxygen therapy. At the enrollment/baseline visit, patients will be consented, randomized, receive their study devices with training (activity monitor, oxygen use diaries, and an assigned POC if randomized to the POC arm), and complete the Visit 1 assessments. At Weeks 1 and 6 after the enrollment/baseline visit, they will receive a phone call from the site to reinforce training on study devices, oxygen usage and study requirements, and adverse event assessment. At the 12-week follow-up/final visit, they will complete an in-clinic visit to return all study devices (POC, activity monitor and oxygen use diaries); have activity monitor device data downloaded by the site; and complete the 12-week assessments. Assessments include a 6MWT, St. George's Respiratory Questionnaire and HADS. Data from the activity monitor will be used to document changes from baseline through 12-week physical activity measures for primary endpoint analysis. Patients will be assessed for adverse events at each encounter after signing the ICF. Study participation is complete when the 12-week follow-up visit is completed.

4 Study Purpose and Objectives

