9.4.1 Physical Activity Level (PAL)

As it relates to the primary study endpoint, PAL will be calculated using the following ratio:

$$\frac{\text{Total Energy Expenditure (TEE) (kcal)}}{\text{Sleep Energy Expenditure (SEE) (kcal)}}$$

The TEE measurement is reported directly by ActiGraph. The baseline calculation will use the average wear-filtered TEE reported within the first week of study participation. The 12-week calculation will use the average wear-filtered TEE reported within the twelfth week of study participation.

The baseline SEE measurement will be derived from average TEE values reported only during the patient's sleep time within the first week of study participation. The 12-week SEE measurement will be

derived from average TEE values reported only during the patient's sleep time within the twelfth week of study participation.

Note: The TEE measurement will also be reported as a stand-alone measurement as a representation of average energy expenditure per day (see section 9.4.4 below).

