10.3 Visit 1: Randomization and Baseline Visit

After a potential study patient has 1) completed the initial informed consent process and signed the study-specific informed consent form, 2) successfully completed the baseline 6MWT, and 3) been determined to meet all inclusion criteria and none of the exclusion criteria, the patient will be randomized in a 1:1 ratio to either SOC long-term oxygen therapy only (control arm) or SOC long-term oxygen therapy plus a POC (treatment arm). Randomization will be stratified by site and will be implemented via small permuted blocks. Randomization assignments will be assigned through the electronic study database and will be obtained by trained site personnel. A patient is considered enrolled at the time of randomization. Patients will be given all study devices relevant to their study arm assignment and will receive training on all devices at the baseline visit. Patients will be instructed to contact their site study staff with any questions pertaining to the study.

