10.3.2 Distribution of Study Devices

During the baseline visit, all patients will receive the following devices:

- ActiGraph activity monitor

In addition to the above devices, treatment arm patients will also receive one POC device.

Patients will be trained on the use of all study-related devices during the baseline visit and will be provided with the associated device instructions/guides for reference. All patients will be instructed to complete oxygen use diaries each day.

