14.4 Other Statistical Considerations

Analysis Data Sets

At a minimum, two distinct analysis sets will be used for the evaluation of primary and secondary effectiveness endpoints. The *intent-to-treat analysis* set will include all randomized patients enrolled in the study. The *per protocol analysis* set will only include patients with complete primary effectiveness endpoint data and no major protocol violations. The safety evaluation will be based on the intent-to-treat analysis set only.

Justification of Pooling Data across Centers

A formal analysis will be conducted to determine the appropriateness of pooling data across the study centers. This will include constructing a linear regression model for the primary effectiveness endpoint with three factors: center, treatment and center by treatment interaction. Furthermore, “super-centers” may be constructed from centers with small numbers of enrolled patients to be entered into models as fixed effects.

Verification of Randomization Procedure

In order to verify the success of the randomization procedure, the distribution of each baseline and demographic variable of interest will be summarized by treatment group. Continuous variables will be summarized via mean, median, standard deviation, and range. Categorical variables will be summarized via counts and frequency distributions.

Missing Data

A sensitivity analysis will be performed for each endpoint to assess the potential impact of missing data on the results. A detailed description of all planned sensitivity analyses can be found in the Statistical Analysis Plan together with the analysis of the relevant endpoints. Missing values will be ignored for the summaries of baseline characteristics, other summaries and safety endpoints.

Standard Statistical Methods

Unless otherwise stated, all *P*-values will be considered significant at a two-sided significance level of 0.05. Summary statistics will be generated for all relevant variables. In the comparison of continuous variables, distributions will be tested for the normality assumption. If standard parametric techniques are found to be inadequate, an appropriate non-parametric technique or a Box-Cox transformation will be used. No corrections will be made for multiple testing procedures. All analyses will be conducted using SAS® version 9.1 or higher.

15 Risk Analysis

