16.4 Device Distribution to/from Patients

Upon being randomized to a study arm, all patients will receive an activity monitor and a diary to record oxygen usage. Patients who are randomized to the treatment arm will also receive the POC device assigned for distribution by his/her specific study site. At the time of device distribution, patients will be informed that they must return all study devices at the end of study participation. Patients are required to return all study devices (POC [if applicable], ActiGraph) to the site at the 12-week visit (or at study termination, if earlier). Sites will return the study devices to Sherpa Clinical Packaging in a bulk shipment at the end of the study. Patients will have the option to purchase their POC device used in the study.

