3.3.4 Randomization

Subjects will be randomized according to the pre-specified randomization schedule following the confirmation of enrollment eligibility. Subjects will be randomized to either the treatment or control arm in a 1:1 ratio. The randomization will be based on random, permuted blocks and stratified by center. Randomization will continue sequentially regardless of a subject not being treated according to their randomization assignment.

4 Study Objectives

This study is designed to evaluate the effect of using a POC combined with SOC long-term oxygen therapy versus SOC long-term oxygen therapy alone on the physical activity level of subjects with COPD requiring long-term oxygen therapy. This study will also assess the effect on oxygen usage, quality of life, hospitalizations, and death and the safety of the device.

5 Endpoints

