5.4 Adverse Events

All adverse events will be recorded and reported.

6 Analysis of Primary Effectiveness Endpoint

The primary effectiveness endpoint analysis evaluates the difference in the mean change in PAL from baseline to the week 12 follow-up visit between the treatment and control arms. For accuracy, only wear-filtered ActiGraph data will be used in the analysis. The baseline PAL uses the average TEE and average SEE values during the first week of the study and the week 12 follow-up visit PAL uses the average values from the twelfth week of the study. Only subjects with available baseline and week 12 follow-up visit PAL values will be included in this analysis.

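### The activity and oxygen-use 'baseline' is the first week after randomisation with the POC already issued, so the primary contrast is the week-12 effect minus the week-1 effect

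*SAP*

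**What the plan says.** The timing follows from several sections read together.

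- **Start of the study clock.** Protocol 10.3: "A patient is considered enrolled at the time of randomization". SAP 11.1.2 also counts the first and twelfth weeks from enrolment.
- **Issue of devices.** Protocol 16.4: "Upon being randomized to a study arm, all patients will receive an activity monitor and a diary to record oxygen usage". Protocol 10.3.2, on the same visit: "In addition to the above devices, treatment arm patients will also receive one POC device". Protocol 3 has patients at that visit "receive their study devices with training (activity monitor, oxygen use diaries, and an assigned POC if randomized to the POC arm").
- **Baseline window.** Protocol 9.4.1: "The baseline calculation will use the average wear-filtered TEE reported within the first week of study participation". SAP 6 repeats it: "The baseline PAL uses the average TEE and average SEE values during the first week of the study". The same first-week window is used for steps (Protocol 9.4.2, SAP 7), oxygen use (SAP 7), change in activity duration and intensity (Protocol 9.4.3, SAP 8) and energy expenditure (Protocol 9.4.4, SAP 8).
- **Primary contrast.** SAP 6 compares mean change in PAL between arms, by t-test or Wilcoxon test (SAP 11.6).
- **Aim.** SAP 4 sets out to "evaluate the effect of using a POC combined with SOC long-term oxygen therapy versus SOC long-term oxygen therapy alone".

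Neither document describes a run-in, or any activity or diary recording before randomisation.

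**The concern.** A change score removes differences between patients that existed before treatment. Here the subtracted value is itself measured on treatment, so any POC effect present in week 1 is subtracted as well. The plan expects the device to be used in that week: the week-1 call checks POC usage (Protocol 10.4), and POC-arm diaries record it daily (SAP 3.2.4).

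Three misreadings are possible. A null result could be reported as showing that adding a POC does not change activity. An effect that is strong early and then fades could appear as harm. And Protocol 14.4 plans, as a check of randomisation, that "the distribution of each baseline and demographic variable of interest will be summarized by treatment group"; if week-1 PAL is among those variables, an early POC effect could be taken for chance imbalance.

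The issue affects PAL, steps and oxygen use, which are tested. It affects energy expenditure and the change summaries of duration and intensity only descriptively, because SAP 8 plans no test for them. The 12-week average duration summary is not a change from week 1 and is unaffected. The 6MWT, SGRQ and HADS are not measured over week 1. The 6MWT must precede randomisation (Protocol 10.3); the order of SGRQ and HADS relative to randomisation is not stated consistently.

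**Working it through.** **1. The plan's own figure.** Inputs from Protocol 14.2 and SAP 6.2: difference 0.1, SD 0.22, two-sided 5%, at least 80% power. A two-sample t-test (noncentral t) needs 76.95, so 77 per arm, with power 80.0%. The plan's 77 reproduces.

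**2. What the contrast estimates.** Let e1 and e12 be the POC effects on mean PAL in weeks 1 and 12. Randomisation makes expected untreated values equal, so

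E[difference in mean change] = e12 − e1.

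Under SAP 6 this applies to patients with both PAL values. A simulation of week-12 minus week-1 change agrees:

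| e1 | e12 | difference in mean change | week-12 difference |
|---|---|---|---|
| 0 | 0.10 | 0.10 | 0.10 |
| 0.05 | 0.10 | 0.05 | 0.10 |
| 0.10 | 0.10 | 0.00 | 0.10 |
| 0.12 | 0.10 | −0.02 | 0.10 |

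**3. Power if part of the effect is early.** Let f be the share of a week-12 effect of 0.1 already present in week 1. The documents do not give f; it is an assumed range. The tested difference is 0.1 × (1 − f). The sample-size text most naturally makes 0.22 the SD of change but does not say so outright. The alternative is that 0.22 is the SD of a single week's PAL. With an assumed week-1/week-12 correlation of 0.7 and equal SDs, the SD of change is then 0.22 × √(2 × 0.3) = 0.170.

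| f | tested difference | power, 77 per arm, SD of change 0.22 | n per arm for 80% | power, 77 per arm, SD of change 0.170 |
|---|---|---|---|---|
| 0 | 0.100 | 80.0% | 77 | 95.1% |
| 25% | 0.075 | 55.6% | 137 | 77.4% |
| 50% | 0.050 | 28.9% | 305 | 44.0% |
| 75% | 0.025 | 10.8% | – | 14.8% |

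At f = 100% the rejection rate is 5%.

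**4. A fading effect (illustration).** With e1 = 0.10, e12 = 0.05 and SD of change 0.22, the tested difference is −0.05. At 77 per arm, the chance of a significant result favouring control is 28.8%, although the POC helps at both times.

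**5. Precision of a week-12 comparison.** With SD of change 0.22 and correlation ρ (assumed), the single-week SD is 0.22/√(2(1 − ρ)). The 95% CI half-width is t(0.975, 152) × SD × √(2/77). Unadjusted, for a week-12 effect of 0.1:

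| ρ | single-week SD | power, 77 per arm | half-width | power, 44/43 |
|---|---|---|---|---|
| 0.5 | 0.220 | 80.0% | 0.070 | 55.4% |
| 0.7 | 0.284 | 58.4% | 0.090 | 36.8% |
| 0.8 | 0.348 | 42.6% | 0.111 | 26.3% |
| 0.9 | 0.492 | 24.1% | 0.157 | 15.5% |

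The change score's half-width is 0.070 throughout. The week-12 comparison has more power when √(2(1 − ρ)) > 1 − f, that is, when f exceeds 22.5%, 36.8% or 55.3% at ρ = 0.7, 0.8 or 0.9.

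The 44/43 split is 109 enrolled (SAP 2) × 0.8 = 87.2, taking 20% loss. At that size the change score (SD 0.22) has power 55%, 35%, 18% and 8% for f = 0, 25%, 50% and 75%. The drop from 77 per arm is due to early closure, not to the baseline definition.

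**The case against.** The best defence is that the SAP follows the protocol faithfully: first-week baseline is the protocol's own definition, and pre-randomisation activity can no longer be collected. No document shows a week-1 effect. If patients take weeks to become more active, e1 is close to zero and the planned contrast is nearly right. Every power loss above depends on an assumed f, and the fading example was chosen to show a reversal. Enrolment stopped at 109, so 137 or 305 per arm is not a practical target. The SAP already plans descriptive statistics (SAP 11.4, 11.6), from which a week-1 or week-12 difference might be worked out. Protocol 14.4 does not name PAL among the variables it will tabulate.

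Most of this stands as a limit on size: this is a risk to interpretation, not a demonstrated bias. It also supports keeping the protocol's analysis. It does not remove the point. A zero week-1 effect is needed for the planned contrast to match the aim, and it is neither stated nor examined. Nothing else in the SAP supplies the check: the missing-data analyses impute only week 12 (SAP 11.5), and the per-protocol set uses the same two weeks. Week-1 PAL as a covariate would not help, because it is also post-treatment.

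**Conclusion.** The concern holds. The value called baseline for PAL, steps, oxygen use, energy expenditure and the change summaries of duration and intensity is an on-treatment week-1 value. The difference in mean change equals the week-12 effect of adding a POC only if the week-1 effect is zero. Otherwise it is too small when the early effect has the same sign, zero when the two are equal, and reversed when the early effect is larger.

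The actual size cannot be computed from the documents; the power figures rest on assumed values of f, on the reading of 0.22 and, for some, on an assumed correlation. Type I error is not inflated if the POC has no effect at any time, and the protocol's success criterion (14.1) does not depend on the test. The consequence is that a null or negative primary result cannot be read as absence of benefit. This should be fixed.

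**What to change.** In SAP 6, and in SAP 7 and 8 for the other affected endpoints:

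1. Keep the protocol-defined change analysis, but label it as change from on-treatment week 1 to week 12. State that it is not the full effect of adding a POC and that a null result does not show no effect.
2. Add a supporting comparison of week-12 PAL by arm with a 95% CI. Adjust for age, baseline 6MWT and centre, the covariates SAP 8 already uses in its Cox model, and not for week-1 PAL. Fix the rule for merging small centres before the model is run, using randomised counts only; for example, centres with fewer than 5 randomised could be merged within POC brand, since each centre supplies one brand. Include every randomised patient with week-12 PAL. This departs from the SAP 11.1.1 analysis set, which requires baseline ActiGraph data, and should apply to this analysis only.
3. Report week-1 PAL by arm with the difference and 95% CI, beside week-1 POC diary use in the POC arm. Present it as a possible early effect, not as a check of randomisation.
4. Do the same for steps and oxygen use, and descriptively for energy expenditure and duration/intensity.
5. Disclose that these analyses were added after closure of an unblinded trial.

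The cost is SAP wording, one added model and one table, all from data already collected. The drawback is precision: the week-12 comparison is less precise than the change score when the week-1/week-12 correlation exceeds 0.5. PAL is total over sleep energy expenditure (SAP 10.1.3), so its level also varies with hours slept, and the gain from covariates is unknown. The comparison should therefore support the primary analysis, not replace it.

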10.5.1 Visit 2 Data Collection

The following information will be collected 12 weeks ± 7 days post-randomization:

- Vital signs
- PaO₂ at rest
- SGRQ questionnaire
- HADS questionnaire
- 6MWT results
- Oxygen usage diary
- Concomitant medications
- Adverse events
- Protocol deviations

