12.2 Patient Withdrawal

A patient may withdraw (or be withdrawn) from the study prematurely for the following reasons:

- Withdrawal of consent by patient
- Withdrawal of patient by investigator
- Lost to follow-up
- Termination of study by the sponsor
- Death
- Other (to be specified).

The reason for termination will be recorded on the appropriate eCRF. In the event that a patient withdraws from the study, a final study visit should be conducted in person. At a minimum, the patient will return all study-related devices and accessories during the final study visit. If the patient wishes to purchase their study POC, they may do so upon study withdrawal. Other final study-related activities (e.g. questionnaire completion) may be conducted at the investigator's discretion and with the patient's agreement.

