11.1 Analysis Sets

11.1.1 Intention-to-Treat

The intention-to-treat analysis set (ITT) consists of randomized subjects who begin long-term oxygen therapy, with or without a POC, receive an ActiGraph device, and have at least baseline ActiGraph data. The ITT analysis set will be used as the primary analysis set in analyzing all endpoints.

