11.5 Handling of Missing Data

A sensitivity analysis will be performed on the primary effectiveness endpoint to assess the effect of missing data. The results using the following imputation methods will be evaluated and compared to the results from the primary analysis:

- Missing week 12 follow-up visit PAL values are imputed with the most recent set of 7 consecutive days with available data from the second half of the 12-week follow-up period (i.e., weeks 7-12)
- Missing week 12 follow-up visit PAL values are imputed with the most recent set of 7 consecutive days with available data from the last quarter of the 12-week follow-up period (i.e., weeks 10-12)

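### The primary PAL analysis is complete-case, and neither planned missing-data analysis covers ITT patients whose activity data stop before the end of week 7

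*SAP*

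**What the plan says.** SAP 6 compares the arms on mean change in PAL from the first to the twelfth week and limits the comparison to complete cases: "Only subjects with available baseline and week 12 follow-up visit PAL values will be included in this analysis". Protocol 9.4.1 fixes the follow-up window in the same way: "The 12-week calculation will use the average wear-filtered TEE reported within the twelfth week of study participation".

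SAP 11.1.1 states: "The ITT analysis set will be used as the primary analysis set in analyzing all endpoints". To belong to that set, a randomised patient must start oxygen therapy, receive an ActiGraph and have baseline ActiGraph data. No follow-up data are required.

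On missing data, Protocol 14.4 says: "A sensitivity analysis will be performed for each endpoint to assess the potential impact of missing data on the results". It leaves the details to the SAP. SAP 11.5 gives two analyses, both for the primary endpoint: "Missing week 12 follow-up visit PAL values are imputed with the most recent set of 7 consecutive days with available data". One searches weeks 7-12, the other weeks 10-12.

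On device return, Protocol 12.2 says of withdrawing patients: "At a minimum, the patient will return all study-related devices and accessories during the final study visit". For patients who complete, Protocol 16.4 says: "Patients are required to return all study devices (POC [if applicable], ActiGraph) to the site at the 12-week visit". Protocol 10.5.1 sets the timing of that visit: "The following information will be collected 12 weeks ± 7 days post-randomization".

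SAP 11.1.2 removes from the per-protocol set any patient with more than two days under 18 hours of wear in week 1 or week 12. That set is used only in a secondary analysis of the primary endpoint.

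**The concern.** PAL is recorded continuously, so a patient who leaves in week 5 has several weeks of post-baseline data. The plan uses none of it for PAL. Such a patient is in the ITT set by definition, is not in the primary analysis, and cannot be imputed under either 11.5 rule. The sensitivity analyses therefore test only losses that occur late, when the carried-forward value is close to week 12. The losses about which least is known are left untested.

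The trial is unblinded, so reasons for leaving could differ between arms. If early leavers differ in activity from those who stay, the complete-case difference is biased, and no planned PAL analysis would show it. Disposition and compliance summaries (SAP 11.4) and the COVID-19-period reasons for missing endpoints (SAP 2) will show how many were lost. They will not show what the loss does to the estimate.

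A smaller, separate matter is visit timing. A patient who attends Visit 2 early but within the window hands back the monitor before the twelfth week is complete, and SAP 6 does not say how a shortened week is treated.

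**Working it through.** **Plan's own figure.** Inputs from SAP 6.2: SD 0.22, difference 0.1, two-sided 5%, 80% power. The two-sample t-test (noncentral t) gives 80.0% power at 77 per arm and 79.5% at 76. The stated 77 per arm (154 in total) is reproduced.

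**Who is reached by each PAL analysis.** The documents do not define day numbering, so two conventions are shown: A counts the randomisation day in week 1 (week 1 = days 0-6); B starts the day after (week 1 = days 1-7).

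| | A | B |
|---|---|---|
| Week 7 | days 42-48 | days 43-49 |
| Week 10 | days 63-69 | days 64-70 |
| Week 12 | days 77-83 | days 78-84 |

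The earliest possible run of seven consecutive days within weeks 7-12 is week 7 itself. Within weeks 10-12 it is week 10 itself. Hence:

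| Data stop | Primary | Weeks 7-12 rule | Weeks 10-12 rule |
|---|---|---|---|
| before end of week 7 (day 48 or 49) | no | no | no |
| later, but before end of week 10 (day 69 or 70) | no | yes | no |
| after week 10, no week-12 data | no | yes | yes |

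Each *yes* also assumes an unbroken seven-day run. The per-protocol analysis adds nobody, because it is a subset of ITT and still needs a week-12 PAL.

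**Possible size of the bias.** In one arm, let a fraction m be missing, with a mean change lower than that of the observed patients by δ. The complete-case mean is then too high by m × δ, and the between-arm difference is biased by m_t δ_t − m_c δ_c. All values below are assumed.

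- Same δ in both arms: bias = δ × gap in missingness. 0.1 × 0.05 = 0.005; 0.2 × 0.10 = 0.02. These are 5% and 20% of the 0.1 target. The δ values are 0.1/0.22 = 0.45 and 0.2/0.22 = 0.91 of the plan's SD.
- Equal missingness of 20%, δ differing by 0.1 between arms: 0.20 × 0.1 = 0.02.

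**Context for numbers analysed.** SAP 2 gives 109 enrolled. With all 109 (55/54), power for 0.1 is 65.2%. With 10%, 20% or 30% missing (assumed, apart from the plan's own 20% attrition), 98, 87 or 76 remain and power is 60.5%, 55.4% or 49.8%. At 20%, 109 − 87 = 22 patients lack a week-12 PAL; the documents do not say how many of these would have stopped before the end of week 7.

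**Visit timing.** Visit 2 may fall on days 84 ± 7, that is 77-91, or 15 days. Full week-12 days at visit day d are min(7, max(0, d − 77)) under A and min(7, max(0, d − 78)) under B.

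| | A | B |
|---|---|---|
| No full day | day 77 | days 77-78 |
| 1-6 full days | days 78-83 | days 79-84 |
| Week cut short, total | 7 of 15 | 8 of 15 |
| Removed by per-protocol rule (4 or fewer full days) | days 77-81 | days 77-82 |

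The last row holds only if days after device return count as non-wear.

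Precision cost of short weeks (assumed: share p of patients has 1-6 days, spread evenly; share f of the change variance is day-to-day noise in a seven-day mean; independent days; approximate because PAL is a ratio). The mean of 7/k over k = 1 to 6 is 2.858, so the variance factor is 1 + 1.858 p f.

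- p = 0.05, f = 0.05: SD 0.2205, power with 55/54 patients 65.0%.
- p = 0.40, f = 0.25: SD 0.240, power 57.9%.

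The loss from 65.2% is therefore 0.2 to 7.3 points. The upper end needs visits spread evenly over the window (6/15 = 0.40) and the largest assumed noise share.

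**The case against.** The complete-case restriction is stated openly, 20% attrition was allowed for, and two sensitivity analyses are planned for PAL. Protocol 14.4 does not promise that every patient will be covered. Study success under Protocol 14.1 requires only that mean change be assessed in both arms. All of this is correct. What remains is that the two analyses are the same carry-forward idea with different reach, so they cannot assess the impact of early loss.

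Several stronger readings are tempting but not supported:

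- *No rule covers a partial or empty week 12.* An empty week is excluded under SAP 6 and imputed under both 11.5 rules. A compliant patient who returns the device on day 77 has days 70-76, which lie inside both windows. For partial weeks, the per-protocol rule removes most short ones in a secondary analysis, on the proviso given above.
- *Every visit that leaves no full week-12 day drops the patient from the primary analysis.* SAP 6 has no full-day requirement. The part-day of return falls in week 12 on day 77 (A) or day 78 (B) and might count as available.
- *Visit timing explains the low power.* The 65.2% reflects early closure and the 55.4% reflects general attrition. Neither measures visit timing.
- *Loss is selective.* The documents show no difference in loss between arms.
- *The primary window should be moved for early attenders.* That would redefine the primary endpoint after closure and would still leave no minimum number of days. It is acceptable only as a supportive analysis.

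**Conclusion.** The concern holds for missing data. ITT patients whose ActiGraph data stop before the end of week 7 enter no PAL analysis, those who stop between then and the end of week 10 enter one, and nothing planned tests departures from missing at random. This follows from the text and does not depend on an assumption beyond the day-numbering convention.

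Its effect on the result is unknown. The bias of 0.005-0.02 (5-20% of the 0.1 target) rests entirely on assumed differences and missingness gaps. At closure only 3 of the 109 enrolled were still active, but the documents do not say how many of the others had left early.

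The visit-timing point is real but carries less weight. It is mainly missing detail: the day numbers of week 12 and the meaning of *available*. Its precision cost is small unless many patients attended early.

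Overall this is an inexpensive improvement that should be made. It does not invalidate the primary analysis.

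**What to change.** 1. Keep the SAP 6 primary analysis and both 11.5 analyses. Add, as a named supportive analysis, a repeated-measures model of weekly PAL change from baseline, with arm, week, arm-by-week and centre, reporting the week-12 difference. It uses every ITT patient with any post-baseline week.
2. Add a delta-adjusted (tipping-point) multiple imputation covering all ITT patients, including those whose data stop before the end of week 7 and those with baseline data only, whom the repeated-measures model cannot use. Vary the shift separately by arm and report where the conclusion changes.
3. State the day numbers of week 12 and which partial weeks count as available. State whether days after a protocol-required device return count as non-compliant for the per-protocol set.
4. Report two further versions as supportive only: one that uses the seven recorded days ending the day before device return where an in-window visit cuts week 12 short, and one with a minimum number of adequate-wear days.

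The activity data are already recorded, so the cost is SAP text and programming. The additions come after closure (effective 30 April 2020; SAP 1.0 is dated 18 Aug 2020) and must be disclosed as such.
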